### **Echocardiogram**

The left ventricular ejection fraction (LVEF) will be measured at screening by echocardiogram.

The data will only be listed: LVEF (%) and the test result as recorded in “Echocardiogram” eCRF page will be provided.

### **ECG and Vital Signs**

The table summarizing ECG and vital signs at baseline will be produced based on ITT analysis set.

The ECG overall assessment as reported by the investigator on the “Electrocardiogram” eCRF page will be summarized at baseline as follows:

- Number and percentage of subjects with result of ECG reported as Normal.
- Number and percentage of subjects with Abnormal result of ECG.

For vital signs, systolic and diastolic blood pressure, heart rate, body temperature, respiratory rate, weight measurements and body surface area (BSA) at baseline will be summarized.

### **Laboratory parameters**

Hematology and biochemistry parameters measured at baseline will also be presented by descriptive statistics. Refer to the section 17.3 for further details.

## **14 Previous or Concomitant Medications/Procedures**

The summaries in this section will be based on the ITT analysis set.

### **14.1 Prior Anti-Cancer Treatment and Procedures**

The prior anti-cancer treatments and procedures are collected under the “Prior anti-cancer drug therapies”, “Prior anti-cancer radiotherapy”, “Prior anti-cancer surgeries”, eCRF pages.

The overall summary of presence of prior anti-cancer treatments/procedures tables will include:

- Number of subjects with at least one prior anti-cancer drug therapy
  - Type of therapy: Cytotoxic therapy / Endocrine therapy / Monoclonal antibodies therapy / Small molecules / Immunotherapy / Other
  - Intent of therapy: Neoadjuvant / Adjuvant / Metastatic or Locally advanced
  - Best response: Complete Response (CR) / Partial Response (PR) / Stable Disease (SD) / Progressive Disease (PD) / Non-Complete Response/Non-Progressive Disease (Non CR/Non PD) / Not assessable / Unknown
- Number of subjects with at least one prior radiotherapy
  - Disease progression in the given previously-irradiated region: yes/no
  - Was the radiotherapy combined with chemotherapy: yes/no
- Number of subjects with at least one prior anti-cancer surgery
  - Curative intent for surgery: yes/no
  - Outcome of surgery: No residual tumor after resection (R0) / Tumor/metastases not resected completely with microscopic residual lesions (R1) / Tumor/metastases not resected completely with macroscopic residual lesions (R2) / Metastases not resected (NR) / Other

An additional table will display a summary of the prior anti-cancer drugs. This summary table will present Anatomical Therapeutic Chemical Classification System (ATC) 2nd level and preferred term of drug name as given from the World Health Organization Drug Dictionary (WHO-DD) current version (by decreasing frequency) based on the incidence in the “Overall” column. In case of equal frequency regarding PT, alphabetical order will be used. In case multiple ATC’s are assigned to a drug, all ATC-2nd level will be used for reporting. A subject will be counted only once within a given drug name, even if he/she received the same medication at different times.

The following listings of prior anti-cancer treatments and procedures will also be provided:

- Listing of prior anti-cancer drug therapies,
- Listing of prior surgeries,
- Listing of prior radiotherapy.

These will include the subject identification number, treatment arm and all the relevant collected data-fields on the corresponding eCRF pages.

## 14.2 Concomitant Medication and Procedures

### *Medications*

Concomitant medications are collected on the “Concomitant medications details” eCRF page and coded using WHO-DD current version.

Traditional Chinese Medicines (TCMs) are a subset of concomitant medications and identified by presence of “TCM” in the medication name as reported by investigator.

According to the concomitant medication start and stop dates, they will be classified as follows:

- Concomitant medications - prior to first treatment: medications stopped before the first dose of trial treatment
- Concomitant medications – on study: medications taken on or after the first dose of trial treatment and within 30 days after last dose of trial treatment. Any medication with start and end dates missing will be considered as on study concomitant medication as well.

Concomitant medications will be summarized as number of subjects with any concomitant medication and also within each ATC-2nd level and preferred term separately for medications prior to first treatment and on study. The summary will be presented by treatment arm and overall based on ITT analysis set.

For TCMs the total number of subjects with any TCM and each TCM (as reported by investigator) will be produced separately for medications prior to first treatment and on study. The summary will be presented by treatment arm and overall based on ITT analysis set.

Concomitant medications will be listed. The listing will include: subject identification number, treatment arm and all corresponding collected data-field on the corresponding eCRF pages, as well as a flag to identify each medication as prior to first treatment or on study.

Premedication, as recorded in “Premedication detail” eCRF page, will be summarized and listed separately. The total number of subjects with any premedication and each premedication (as reported by investigator) will be produced.

### ***Procedures***

Concurrent procedures are reported on the “Concomitant procedures details” eCRF page, will be coded using the most recent MedDRA version.

According to the procedure start and stop dates, they will be classified as follows:

- Concurrent procedures - prior to first treatment: procedures stopped before the first dose of trial treatment
- Concurrent procedures - on study: procedures taken on or after the first dose of trial treatment and within 30 days after last dose of trial treatment. Any procedure with start and end dates missing will be considered as on study concurrent procedure as well.

The concurrent procedures will be summarized based on ITT population per treatment arm and overall separately for procedures prior to first treatment and on study. The number and percentage of subjects within each MedDRA SOC (ordered alphabetically) and PT (ordered alphabetically) will be displayed. The reason for procedures will be summarized.

Concurrent procedures will also be listed including: subject identification number, treatment arm and all corresponding collected data-field on the corresponding eCRF page and also coding information. A flag will be added to identify each procedure as prior to first treatment and on study.

## **14.3 Anti-Cancer Treatment after Discontinuation**

The data collected from the “Anti-cancer treatment after discontinuation” eCRF page will be listed.

The anti-cancer treatments after discontinuation will also be summarized in terms of:

Number of subjects with at least one anti-cancer drug therapy after discontinuation

- Type of therapy: Cytotoxic therapy / Endocrine therapy / Monoclonal antibodies therapy / Small molecules / Immunotherapy / Other
- Intent of therapy: Neoadjuvant / Adjuvant / Metastatic or Locally advanced
- For the Metastatic or Locally Advanced Intent, the number of subjects with each Line of treatment will be presented
- Best response: Complete Response (CR) / Partial Response (PR) / Stable Disease (SD) / Progressive Disease (PD) / Non-Complete Response/Non-Progressive Disease (Non CR/Non PD) / Not assessable / Unknown

## 15 Treatment Compliance and Exposure

The extent of exposure for cetuximab, cisplatin, carboplatin, and 5-FU will be characterized by duration (weeks), number of initiated cycles, cumulative dose, dose intensity, relative dose intensity, number of dose reductions and dose delays, drug discontinuation. Descriptive statistics will be used to summarize treatment exposure, based on the eCRF data. Summaries will be performed on the safety analysis set.

All dosing calculations and summaries will be based on “cetuximab Initial Administration”, “Cetuximab Administration”, “Cisplatin Administration”, “Carboplatin Administration”, and “5-FU Administration” eCRF pages.

### 15.1 Cetuximab Exposure

.Analysis of cetuximab exposure will be based on the calculated actual dose levels (total dose administered (mg) / BSA (body surface area in m^2)). For total dose administered, the actual dose administered as entered in the eCRF pages will be used. For BSA, BSA value collected on the “BSA Determination” eCRF page will be used. The last available BSA of the subject on or prior to the day of cetuximab dosing will be used. The duration of cetuximab treatment (in weeks) during the study is defined as:

$$\text{duration of cetuximab} = \left( \frac{(\text{date of last dose of cetuximab} - \text{date of first dose of cetuximab}) + 7}{7} \right)$$

The total number of cetuximab infusions per subject is the count of the infusions with non-zero dose of cetuximab that the subject received.

The cumulative actual treatment dose (mg/m^2) of cetuximab per subject is the sum of the calculated actual dose levels of cetuximab that the subject received.

The dose intensity of cetuximab (mg/m^2/week) per subject from the second infusion is defined as:

$$\left( \frac{\text{Cumulative dose of cetuximab from 1st infusion} - \text{initial dose of cetuximab}}{((\text{date of last dose of cetuximab} - \text{date of second dose of cetuximab}) + 7) / 7} \right)$$

The relative dose intensity of cetuximab (%) starting from the second infusion is defined as the dose intensity of cetuximab defined in the preceding formula divided by 250 mg/m^2/week (the planned weekly dose as assigned in the protocol) and multiply by 100. Therefore the dose intensity and the relative dose intensity are only calculated for subjects who received at least 2 dosages of cetuximab.

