Duration of treatment for subjects in Arm A: Subjects with absence of PD, as assessed by the Investigator, and unacceptable toxicity will receive a maximum of 6 cycles of chemotherapy (cisplatin plus 5-FU) and cetuximab weekly. Subjects who have not experienced PD after end of chemotherapy will continue treatment with cetuximab until either PD, as assessed by the

Investigator, or occurrence of an unacceptable toxicity. Subjects with an unacceptable toxicity due to one of the trial drugs will receive other trial drug(s) without unacceptable toxicity until either PD or completion of 6 cycles of chemotherapy. If treatment with cetuximab is delayed because of a related toxicity, the 21-day rhythm of chemotherapy is retained. A maximum of 2 consecutive cetuximab infusions can be withheld (no more than 21+3 days without cetuximab infusions) due to unacceptable toxicity, otherwise the subject must stop cetuximab. If treatment is delayed because of toxic effects of the chemotherapy, the 7-day rhythm of cetuximab infusions is retained. Chemotherapy can be delayed for a maximum of 21+3 days; after this, the subject must stop the chemotherapy treatment. The subject may continue on cetuximab monotherapy (if still benefiting).

Duration of treatment for subjects in Arm B: Subjects with absence of PD, as assessed by the Investigator, and unacceptable toxicity will receive a maximum of 6 cycles of chemotherapy. Subjects with an unacceptable toxicity due to one of the trial drugs will receive other trial drug(s) without unacceptable toxicity until either PD, as assessed by the Investigator, or completion of 6 cycles of chemotherapy. Chemotherapy can be delayed for a maximum of 21+3 days; after this, the subject must stop the chemotherapy treatment.

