6.2.1 Selection and Timing of Cetuximab

Subjects in Arm A only, will receive cetuximab in combination with cisplatin or carboplatin plus 5-FU chemotherapy. Cetuximab will be given every 7 days as outlined in Table 6.1.

Table 6.1 Dose and Administration Procedure for Cetuximab

	Dosage	Infusion rate	Flush of line with saline solution (0.9%) at the end of infusion	Prophylactic pretreatment with an appropriate antihistamine and corticosteroid
First infusion	400 mg/m ²	maximum 5 mg/minute	Yes	Mandatory
Subsequent infusions	250 mg/m ²	maximum 10 mg/minute	Yes	Recommend

The cetuximab dose will be based on the subject's BSA and has to be recalculated and the dose adjusted accordingly before each cetuximab infusion. The BSA should be calculated according to the Mosteller formula: BSA (m^2) = sqrt ([height (cm) × weight (kg)] / 3600). The calculation will be based on the weight measured at each relevant visit and the height as measured and recorded at the screening visit.

The maximum infusion rate must NOT exceed 5 mg/minute for first infusion and must NOT exceed 10 mg/minute at subsequent infusions.

Cetuximab will always be administered before cisplatin or carboplatin on Day 1 of a cycle. Cetuximab infusions should be performed, if possible, on the same day of each week with no more than 3 days deviation.

Pretreatment with an appropriate antihistamine and a corticosteroid are mandatory at least 1 hour before the first cetuximab administration and these premedications are recommended before all subsequent infusions of cetuximab (see Section 6.4.2).

Before, during, and up to 1 hour after each cetuximab infusion, subjects must have their vital signs continuously monitored to detect any AEs (specifically, allergic/hypersensitivity reactions). A physician should be available during each cetuximab administration, i.e., until the complete infusion has been given and for 1 hour after the end of the infusion. Exact documentation of actual dose, date, start time, and end time of each cetuximab infusion is mandatory.

Cetuximab must not be mixed with any other substance and therefore requires a separate infusion line. If another intravenous infusion is required at the same time as the cetuximab infusion (e.g., for hydration), a second line must be used.

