## Delays

Cetuximab should be administered, if possible, on the same day of each week with no more than 3 days deviation. From there, a delay will be defined as a period of more than 10 days between 2 subsequent infusions (from the second infusion). The number of days delay will be calculated as follows:

$$[\text{date of infusion (i)} - \text{date of infusion (i-1)}] - 10 \text{ days, where } i=2,3,..I$$

If the value above is >0 days, then this will be classed as a delay. A subject may have more than one treatment delay throughout the course of treatment.

The summary of cetuximab treatment exposure table will include the following information:

- Duration of cetuximab therapy (weeks): summary statistics.
- Number of initiated cycles for cetuximab: summary statistics
- Total number of cetuximab infusions received: number of subjects with 0, 1, 2, 3, 4, 5, 6, 7, 8, 9, 10, >10 infusions
- Cumulative actual treatment dose of cetuximab (mg/m^2): summary statistics.
- Dose intensity of cetuximab (mg/m^2/week) excluding initial dose: summary statistics.
- Relative dose intensity of cetuximab (%) excluding initial dose: < 60%, 60% - < 80%, 80% - < 90%, 90% - 110%, > 110%.
- Number of subjects per minimum relative dose category (as defined Section 15.1)
- Number of subjects with at least one delayed cetuximab infusion, and maximum length of delay (no delay including 1-2 days delay, 3-8 days, 9-15 days, ≥16 days) – worst case

A listing will detail cetuximab exposure for each subject based on “Cetuximab administration” eCRF page.

In addition, batch numbers data, as recorded in “Accountability Group A” eCRF page will be listed.

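### SAP 15.1 starts the cetuximab dose-intensity clock at the actual second infusion, so a delay right after the loading dose never lowers relative dose intensity

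*SAP*

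**What the plan says.** SAP Section 15.1 builds cetuximab dose intensity from "Cumulative dose of cetuximab from 1st infusion" minus the initial dose, divided by a number of weeks. Those weeks run from the "date of second dose of cetuximab" to the last dose, plus 7 days. On relative dose intensity (RDI) the section reads: "The relative dose intensity of cetuximab (%) starting from the second infusion is defined as the dose intensity" so obtained, over 250 mg/m² per week, and only subjects with at least two doses get one. The summary list in the same section calls the item "Relative dose intensity of cetuximab (%) excluding initial dose" and reports it in the bands below 60%, 60 to <80%, 80 to <90%, 90 to 110% and above 110%.

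Protocol Section 6.2.1 sets the planned schedule: "Cetuximab will be given every 7 days as outlined in Table 6.1". The second infusion is therefore due 7 days after the first. Protocol Section 5.1 limits interruptions: "A maximum of 2 consecutive cetuximab infusions can be withheld", with no more than 21+3 days between infusions. Protocol Section 8.5.4 describes RDI as actual dose over planned dose, and SAP Section 9 declares no change from the protocol.

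Other parts of the SAP do count time from the first dose. Cetuximab treatment duration does (15.1), and so do the durations used for cisplatin, carboplatin and 5-FU dose intensity (15.2 to 15.4). The cetuximab delay formula runs from i=2, so it includes the interval from infusion 1 to infusion 2.

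**The concern.** Leaving the loading dose out of the numerator is a stated choice. Leaving out the waiting time after it is not explained anywhere. Infusions due on Day 8 and Day 15 are planned maintenance doses. If they are withheld before the second infusion is given, the SAP formula treats them as never planned.

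Two subjects with identical doses over an identical calendar period can therefore have different RDIs, depending only on where the gap fell. One subject can also show a delay of 9–15 days beside an RDI of 100%.

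An early hold is plausible. Protocol Section 3.7.4 places most skin reactions in the first 3 weeks. Section 6.2.2.1 lets a Grade 3 skin reaction lead to omission of one or two administrations, and for the first such event the dose level is unchanged. At stake is how faithfully the exposure table describes cetuximab delivery in Arm A.

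**Working it through.** The SAP states no numeric RDI, so there is no figure to reproduce. The check compares its formula with one tied to the planned schedule.

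**Inputs**
- Planned interval 7 days (Protocol 6.2.1).
- Reference 250 mg/m² per week, and the numerator and denominator as defined in SAP 15.1.
- m = infusions withheld between infusions 1 and 2; at most 2 (Protocol 5.1).
- k = full weekly infusions after the loading dose. This is an assumption: the documents give no distribution of k. The range 1 to 20 is shown.

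**Formulas** (C = cumulative dose, D1 = initial dose, dates in days)
- SAP: RDI = 100 × (C − D1) / {[(last − second) + 7]/7} / 250
- Planned schedule: RDI = 100 × (C − D1) / {[(last − (first + 7)) + 7]/7} / 250

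Here C − D1 = 250k, second = first + 7(m+1) and last = second + 7(k−1). The SAP denominator is [7(k−1) + 7]/7 = k weeks. The planned-schedule denominator is [7(m+1) + 7(k−1)]/7 = k+m weeks. The SAP therefore gives 100% for every k and m, and the planned schedule gives 100k/(k+m)%.

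| k | SAP | Planned, m=1 | Planned, m=2 |
|---|---|---|---|
| 1 | 100% | 50.0% | 33.3% |
| 5 | 100% | 83.3% | 71.4% |
| 10 | 100% | 90.9% | 83.3% |
| 15 | 100% | 93.8% | 88.2% |
| 20 | 100% | 95.2% | 90.9% |

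With m=2, k=15 corresponds to an 18-week course: 18 planned infusions, less two withheld, less the loading dose. The subject stays in the 90–110% band when k/(k+m) ≥ 0.9, that is k ≥ 9m: nine or more later doses for m=1, 18 or more for m=2.

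**Same doses, different timing (k=5, two infusions withheld)**
- Early gap: Days 1, 22, 29, 36, 43, 50. SAP denominator (50 − 22 + 7)/7 = 5 weeks; 1250/5/250 = 100%.
- Later gap: Days 1, 8, 15, 36, 43, 50. SAP denominator (50 − 8 + 7)/7 = 7 weeks; 1250/7/250 = 71.4%.

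Both subjects received the same total dose between Day 1 and Day 50, yet one falls in 90–110% and the other in 60 to <80%.

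**What the rest of the table shows for the early-gap subject**
- Delay: 21 − 10 = 11 days, category 9–15 days.
- Duration: (50 − 1 + 7)/7 = 8 weeks, against 6 infusions.

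**Sensitivity**
- Loading dose counted on both sides: (400 + 5×250)/(400 + 7×250) = 1650/2150 = 76.7%, so the result does not depend on excluding it.
- A 24-day gap (the 21+3 limit): 7/24 = 29.2% at k=1; 35/52 = 67.3% at k=5.

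**The case against.** The strongest defence is that the SAP declares its window. It says the measure starts from the second infusion, and numerator and denominator cover the same stretch of maintenance treatment. Protocol 8.5.4 gives actual over planned dose without a time base and leaves further safety-analysis detail to the SAP. The early gap is also reported in the same table through the delay summary and the duration, and again in the subject listing. All of this is true. It limits the consequence, but it does not make 100% the right value: the declared window explains why the loading dose is excluded, not why maintenance doses due on Days 8 and 15 stop being planned.

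The frequency argument also deserves weight. The effect needs a hold before infusion 2, due on about Day 8. The statement about skin reactions in the first 3 weeks covers all grades over 21 days, while delay is provided for at Grade 3. A reader might add infusion-related reactions as a cause, since they occur mainly with the first infusion. Table 6.3 does not support that: Grades 1 and 2 are handled within the infusion, and Grades 3 and 4 end cetuximab, so those first-infusion cases have no second dose and no RDI.

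A reader might also infer that the formula errs upward in every case. It does so for late second infusions. The protocol allows 3 days' deviation, and if infusion 2 is 3 days early with k=5, the planned-schedule value is 5/(32/7) = 109.4% against the SAP's 100%.

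**Conclusion.** The point holds as a minor one. The SAP formula makes RDI blind to a delay between the loading dose and the second infusion, and this is inconsistent with its treatment of later delays. The overstatement is the difference between 100% and k/(k+m), assuming full doses weekly after the gap. The number of affected subjects cannot be known from the documents.

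Three stronger readings are not supported:
- That 71% is a floor. It is the single case m=2, k=5; the value is lower for shorter courses and about 88–91% at k=15 to 20.
- That RDI is the trial's principal evidence on cetuximab delivery. It is one of several descriptive exposure items, and the stated aim is efficacy and safety.
- That the issue touches the efficacy conclusion. PFS by independent review, its hazard ratio and the 0.77 criterion do not use RDI.

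**What to change.** Keep the numerator. Change the denominator in SAP 15.1 to ((last dose − min(second dose, first dose + 7)) + 7)/7 weeks.

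When infusion 2 is on time or early this equals the present formula; when it is late the delay is counted. The simpler form (last − first)/7 is less suitable, because with k=1 and a second infusion 4 days after the first it would give 7/4 = 175%.

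The cost is one formula in the SAP and one line in the exposure program. RDI becomes slightly less favourable for subjects with a late second infusion, including those late but within the 3-day window. It is also sensitive to that one interval when few infusions were given: a 10-day interval gives 7/10 = 70% at k=1, but 35/38 = 92.1% at k=5.

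If the sponsor keeps the present formula, the SAP and a table footnote should say that the interval between infusions 1 and 2 is excluded.

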### Dose reductions

The minimum doses of trial drugs will be derived per subject and clustered according to the proportions of the planned dose. The minimum dose levels will be categorized as follows:

| Minimum relative dose | Cetuximab*           | Cisplatin            | 5-FU                      | Carboplatin |
|-----------------------|----------------------|----------------------|---------------------------|-------------|
|                       | (mg/m  ) | (mg/m  ) | (mg/ m  /day) |             |

| 100 % (planned dose) | 250        | 75           | 750        | AUC 5   |
|----------------------|------------|--------------|------------|---|
| ≥ 90%                | ≥225       | ≥67.5        | ≥675       | Based on
planned dose
given in the
CRF |
| ≥70 - <90%           | 175 - <225 | 52.5 - <67.5 | 525 - <675 |   |
| ≥50 - <70%           | 125 - <175 | 37.5 - <52.5 | 375 - <525 |   |
| <50%                 | <125       | <37.5        | <375       |   |

\*Initial dose will be omitted

